8.7. Follow-up of adverse events

All SAEs will be followed until they have abated, or until a stable situation has been reached. Depending on the event, follow up may require additional tests or medical procedures as indicated, and/or referral to the general physician or a medical specialist.

SAEs need to be reported from the first administration of treatment according to protocol until day 14 days after the last dose of the IMP or until the start of subsequent systemic therapy for the disease under study, if earlier.

8.8. Data Safety Monitoring

No data safety monitoring board (DSMB) will be implemented because the investigational product has been very well tolerated in the phase II and III studies and a previous fase III trial did not show any increase in AE or SAE in the anidulafungin voriconazole combination arm compared with the voriconazole monotherapy arm.

9. STATISTICAL ANALYSIS

9.1. Primary endpoint analysis

The primary endpoint is defined as all-cause mortality at 42 days (6 weeks) after randomization. The MITT population is considered the main analysis population.

The relation between randomly allocated treatment and the incidence of the primary endpoint in the MITT population will be described by

- the total number of endpoint events by allocated treatment;
 - a crude, unadjusted odds ratio. Logistic regression analysis will be conducted, with randomly allocated treatment as independent predictor variable and the incidence of the primary endpoint as dependent outcome variable;
 - an adjusted odds ratio. A multivariable logistic regression analysis will be applied. The effect of randomly allocated treatment will be adjusted for age, pulmonary or (also) extrapulmonary disease, ICU admission, baseline serum galactomannan status, post allogeneic stem cell transplantation status, and acute or chronic GVHD for which patients are receiving systemic immunosuppressive therapy.

The adjusted odds ratio will be considered the key primary endpoint analysis

The same analysis will be performed for secondary endpoints 2 to 6. The listed sub-populations will be analyzed using simple and multivariable logistic regression (the adjustment factors - as far as applicable - are listed above). Since these analyses will be considered exploratory only and these endpoints are defined as secondary endpoints, no correction for multiple testing will be performed.

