7.1.4. Definitions of the patient populations

ITT: All patients randomized as registered in the IVRS

MITT: All patients randomized as registered in the IVRS, in whom the positive mycological test was available at the time of randomization or became available within 8 days after randomization will be included in the MITT population unless resistance to voriconazole was documented by culture or PCR (VIPcheck or Aspergenius, see below). Because Dutch guidelines currently recommend initiating combination antifungal therapy if the presence of an azole resistant A. fumigatus infection cannot be excluded by PCR or culture, Dutch patients in whom the resistance PCR or culture turns out unsuccessful will be excluded from the MITT population as well. The antifungal therapy given to these patients will be decided upon by their treating physician (see also flowdiagram).

ICU population: Patients already admitted to the ICU at the time of the start of triazole antifungal therapy

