9.3. Multiplicity

There is only 1 primary endpoint and no interim analysis for efficacy will be performed. Therefore, the primary endpoint will be tested at the α =0.05 level (two-sided test).

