9.5. Sample size calculation

In the pivotal trial on voriconazole and anidulafungin combination therapy the mortality in the voriconazole control group was 28% 6 weeks after the start of therapy. This study only included patients with an underlying haematological disease. Furthermore, in a large pragmatic trial with fewer exclusion criteria and in which a small number of ICU patients will be included as well, we expect a somewhat higher mortality of 35%, We consider a 33% lower overall mortality with combination therapy (=from 35% to 23,33%) compared to monotherapy of clinical importance. This leads to a sample size of 237 evaluable patients per group (=included in the mITT population as defined above) to show superiority of combination therapy compared with monotherapy with an alfa of 0.05 and a power of 80%. Follow-up for the primary endpoint is 6 weeks after the start of antifungal therapy.

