APPENDIX 2: PATIENT VISIT SCHEDULE

	Screening	Baseline (D1)	D2-6	D3	D5	D7	D8-D28	D14	D28	D42	D84	D168	D8-28
Eligibility check ^(#)	Х	X ^(#)											
Informed consent		Х											
Study drug administration ^(^)		Х	Х			Х	(x)						Х
Medical history		Х											
Serum sampling ^(*)		Х		Х	х	Х		Х	Х				
Patiënt details		Х											
Register use of any antifungals		Х						Х	Х	Х	Х	Х	
Register use of TPV or EN after baseline visit										Х		Х	
Register use of any blood products administered after baseline visit										Х		Х	
Register hospital and ICU days from baseline to week 24										Х		Х	
Quality of life questionnaire		Х								х	х	Х	
Loss of income questionnaire		Х									х	Х	
Neutropenic status		Х				Х		х	х	х	х		
Survival status						Х		Х	Х	Х	Х	Х	

Please note that few exceptions notwithstanding, screening and baseline visit will be done on the same day.

Gray columns indicate the days that a hospital visit is required: Although the large majority of the patients will be in the hospital during the first week of therapy some patients will be outpatients. Patients who are outpatients and are included in the study are required to visit the outpatient clinic for study drug administration up until day 7.

Please note that, except for the screening and baseline visit, none of the other visits require an additional patient visit to the hospital as all these data can be collected from the patient files and by contacting the patient or the general practitioner or relatives of the patient.

(°) For the patients randomized in the combination therapy group. The minimum duration of study drug treatment is 7 days. After day 7 and up until day 28 the investigator decides if the treatment needs to be continued for a maximum of 28 days.

(#) For ICU patients the SOFA score should be recalculated if >24hrs pass between screening and baseline and patient excluded if SOFA has increased to >11 points.

(*) This should only be done if the patient is still in the hospital or visiting the outpatient clinic at these study dates. Please note that the day 14 and day 28 sampling can be done between day 11 and 17 and day 25 and 31 respectively (so day 14±3days and day 29±3days). The standard operating procedure regarding serum sampling and storage of serum by the lab is described in appendix 6 in more detail.

TPV= total parenteral nutrition. EN= enteral nutrition.

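### Baseline neutropenic status is collected for every patient but is not in the key adjusted model; adding it is a cheap, optional improvement

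*Protocol*

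**What the plan says.** Protocol Section 9.1 names the adjusted odds ratio as the key primary analysis and lists the adjustment factors: "The effect of randomly allocated treatment will be adjusted for age, pulmonary or (also) extrapulmonary disease, ICU admission, baseline serum galactomannan status", then post-allogeneic transplant status and GVHD under systemic immunosuppression. That makes six factors. The same model is to be used for secondary endpoints 2 to 6, with the factors applied where they make sense.

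Appendix 2 has a row "Neutropenic status", marked at baseline (D1) and at D7, D14, D28, D42 and D84, with no restriction to a subgroup. Appendix 1 puts neutropenia first among the host factors and lets newly diagnosed AML count as neutropenic. Section 7.2 stratifies randomisation by AML, GVHD and other.

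The design figures are in Sections 9.3 and 9.5: a control-group expectation ("we expect a somewhat higher mortality of 35" per cent), a "33% lower overall mortality with combination therapy (=from 35% to 23,33" per cent effect, and a "sample size of 237 evaluable patients per group" "with an alfa of 0.05 and a power of 80" per cent, tested at the 0.05 "level (two-sided test").

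**The concern.** The protocol settles the covariate list itself, so the list can be judged here. It leaves out a baseline characteristic that the trial collects anyway and that the protocol treats as a main route into the disease. Nothing else in the model carries that information. The only haematological terms are transplant status and treated GVHD, so patients under AML chemotherapy are not separated from the rest. AML would also be an imperfect substitute: new AML is deemed neutropenic by rule, whereas a patient in a later treatment phase may or may not be.

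If neutropenia predicts death, leaving it out gives up a little power. It also lets a chance imbalance between arms move the odds ratio that the protocol calls its key result. A covariate added once results by arm are known would be hard to defend. The trial is open-label, has no data safety monitoring board (Section 8.8), and the study team itself meets if the interim conditional power is below 10% (Section 7.7).

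**Working it through.** **1. The plan's own figure.** Inputs from Sections 9.3 and 9.5: p1 = 0.35, p2 = 0.2333, two-sided alpha 0.05 (z = 1.960), power 80% (z = 0.8416). With the pooled variance under the null and no continuity correction,

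n = [1.960 × √(2·p̄·(1−p̄)) + 0.8416 × √(p1(1−p1) + p2(1−p2))]² / (p1−p2)², where p̄ = 0.29165.

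- First term: 1.960 × √0.4132 = 1.2598
- Second term: 0.8416 × √(0.2275 + 0.1789) = 0.5365
- n = 1.7964² / 0.1167² = 3.2269 / 0.013619 = 236.9, so 237 per group

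Power at 237 per group is 0.800. The calculation uses no covariate, so the design power does not depend on the covariate list.

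**2. What adding one binary baseline covariate does to power.** The documents give neither the share of neutropenic patients nor their relative mortality, so both are assumed. Simulated trials had 237 per arm and mortality of 35% versus 23.3%, with 3,000 runs per setting.

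| Assumed odds ratio for death | 30% neutropenic, treatment-only model plus neutropenia | 50% neutropenic, treatment-only model plus neutropenia | 50% neutropenic, existing covariates plus neutropenia |
|---|---|---|---|
| 1 | 81.0 → 80.6% | 80.2 → 80.2% | not run |
| 1.5 | 80.9 → 81.2% | 79.2 → 79.5% | 81.3 → 82.0% |
| 2 | 79.5 → 80.3% | 80.6 → 81.0% | 81.5 → 82.7% |
| 3 | 81.0 → 82.9% | 80.3 → 82.3% | 82.8 → 85.3% |

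Over odds ratios of 1 to 3 the gain runs from about 0 to 2.5 points. At an odds ratio of 4, in the treatment-only setting, it is about 3 to 4 points.

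**3. Standard error.** In the treatment-only setting the standard error of the log odds ratio goes from 0.206 to 0.209 at an odds ratio of 2, and to 0.213 at 3. The estimate moves further from zero, for example from −0.568 to −0.604 at an odds ratio of 3 and 50% prevalence. The ratio of estimate to standard error rises from 0.568/0.2061 = 2.76 to 0.604/0.2130 = 2.84. The gain is in power, not in a narrower standard error.

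**4. Type I error.** Under no treatment effect, rejection rates with and without the covariate differ by at most 0.3 points and lie between 4.6% and 5.1%. The exception is one setting with a covariate unrelated to death, where both models gave 6.3%; I read that as simulation noise.

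**5. Chance imbalance.** The difference in prevalence between arms has standard error √(2·q(1−q)/237). For q = 0.5, 1.96 × √(0.5/237) = 0.090. For q = 0.3, 1.96 × √(0.42/237) = 0.083. So one trial in 20 would show an imbalance of about 8 to 9 points or more, if neutropenia were independent of the randomisation strata. The simulated shift in the log odds ratio per unit of imbalance is 0.69 at an odds ratio of 2 and 1.07 at 3. At 0.09 this gives exp(0.69 × 0.09) = 1.06 and exp(1.07 × 0.09) = 1.10, a shift of about 6% to 10%.

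**6. Room in the model.** Expected deaths: 237 × (0.35 + 0.2333) = 138. Treatment, six factors and neutropenia make eight terms if each takes one degree of freedom: 138 / 8 ≈ 17 deaths per term.

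**The case against.** The strongest reply is that nothing is wrong. Six baseline covariates are prespecified, which is good practice, and any list could be longer. The prognostic value of neutropenia is assumed, and at odds ratios of 1 to 1.5 the gain is negligible. Chance imbalance is already allowed for in the 5% error rate. The imbalance figures are also too large to the extent that stratifying by AML, which overlaps with neutropenia, balances it. All of this stands, and it is why the point is optional. What remains is that the information is already collected, has no proxy in the model and costs one degree of freedom.

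A reader might infer that the omission costs precision or leaves the trial underpowered. Steps 1 and 3 show otherwise.

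A reader might also want country in the model, because "Dutch patients in whom the resistance PCR or culture turns out unsuccessful will be excluded from the MITT population as well" (Section 7.1.4) while Belgian patients in that position stay, and exclusion criterion 6 applies only in the Netherlands. The documents do not support that step. Apart from that entry criterion, country matters only when resistance testing is unsuccessful; documented resistance and the lack of a positive mycological test remove patients in both countries. The Dutch rule is written the same way for both arms. No mortality by country is given, so no size can be put on the gain, and a country term would not undo the selection.

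Finally, the stratification factor itself is only partly in the model, since AML is absent. That is a separate question, which a neutropenia term does not settle.

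**Conclusion.** The key model omits a recorded baseline characteristic that no other term represents. This is a missed small gain, not an error: the 237 per group, the 80% power and the type I error all stand. If the odds ratio of neutropenia for death lies between 1 and 3, which is an assumption, adding it is worth about 0 to 2.5 points of power. At an odds ratio of 2 to 3 it also removes a shift of about 6% to 10% in the treatment odds ratio in the 1-in-20 trials with the largest imbalance; stratification by AML makes such imbalances somewhat rarer. The statistical analysis plan was not available; if it already includes the term, the point is met.

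**What to change.** In Section 9.1, add baseline neutropenic status (yes/no, as recorded at D1) to the covariates of the adjusted model for the primary endpoint. State what a yes means, because Appendix 2 does not define the item and Appendix 1 mixes recent, ongoing and deemed neutropenia. Use only the D1 value, since later values are post-randomisation.

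For secondary endpoints 2 to 6, include the term only as far as the number of deaths allows. The count of 138 applies to the full MITT population at 6 weeks; the subgroups in endpoints 3 to 6 will have fewer deaths, and neutropenia may be rare among patients without haematological disease (endpoint 6).

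Fix the change before any look at results by arm, including the interim futility analysis. The cost is one sentence, one degree of freedom and possible sparseness in the smaller subgroups; no new data are needed. Leave country out of the model; the treatment effect by country may be shown descriptively.

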7.1.2. Secondary study endpoints

- 1. Overall aspergillus attributable mortality 12 weeks after the start of antifungal therapy(*).
- 2. Overall survival 12 weeks after the start of antifungal therapy in the MITT population
- 3. Overall survival 6 weeks after the start of therapy in the subgroup of patients in the MITT population with a positive serum galactomannan test at baseline.
- 4. Overall survival 6 weeks after the start of therapy in the subgroup of non-ICU patients who fulfill the EORTC/MSG probable or proven definition (MITT population).
- 5. Overall survival 6 weeks after the start of therapy in the subgroup of non-ICU patients with an underlying haematological disease (MITT population)
- 6. Overall survival 6 weeks after the start of therapy in the subgroup of non-ICU patients without an underlying haematological disease (MITT population)
- 7. Overall survival 6 weeks after the start of therapy in patients that started with triazole monotherapy and in which triazole resistance is detected during follow-up (MITT population)
- 8. Overall survival 6 weeks after the start of therapy in patients that started with triazole-anidulafungin combination therapy and in which triazole resistance is detected during follow-up (MITT population)
- 9. In the subgroup of patients with a positive serum galactomannan; Kinetics of serum galactomannan levels with combination versus monotherapy
- 10. Outcome of patients in which resistance testing was unsuccessful
- 11. Time to hospital discharge (in the MITT subgroup of patients admitted to the hospital at baseline)
- 12. Cost-effectivity of azole-anidulafungin combination therapy
- (*) Aspergillus attributable mortality is defined according to Vidal G et al. (with some modifications) as one of the following²²:

When selecting one of the 4 options below, please consider the immediate cause of death as the disease process, injury, or complication immediately preceding death.

IA is considered the cause of death (=IA attributable mortality)

1. IA was considered the cause of death when the immediate cause of death was due to this infection. Examples are neurological complications of an aspergillus infection

- that disseminated to the brain, lung bleeding or respiratory insufficiency in a patient with pulmonary aspergillosis *or*

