7.1.3. Pragmatic study design

We have tried to design the study in such a way that the prompt inclusion of patients is facilitated as much as possible.

- 1. Registration trials of new antifungal drugs typically only include patients that fulfill the strict lung CT radiology criteria (e.g. halo sign) as described in appendix 1. However, in real-life as much as 50% of the patients treated for invasive aspergillosis do not have these typical abnormalities but are treated on the basis of the presence of a host factor, a positive mycological test and a (non-typical) pulmonary infiltrate. The outcome of these patients is similar to those with the typical pulmonary infiltrate. ¹² Therefore, we consider the exclusion of these patients undesirable in the context of a pragmatic trial.
- 2. Typically, patients that have received antifungal therapy for more than 48-96 hours at the time of inclusion are excluded from registration trials. Again, this leads to many patients being excluded from study participation. To avoid this, we will allow that patients at high risk of IA (patents with AML or grade II or higher GVHD) are included at the time the triazole antifungal therapy is initiated by the treating physician even when the mycological criterium is not yet met. These patients will

- be followed until day 7 and will leave the study if at that time the mycological tests have turned out to be negative.
- 3. While the previous randomized study on the use of combination antifungal therapy for IA only included patients with an underlying haematological disease, there is no reason to believe that the hypothesis of improved survival with combination therapy only applies to these patients. Therefore, our study population will not be limited to this subgroup of patients.
- 4. Our study design has overall mortality as the primary endpoint and no compulsory follow-up CT scans are required.
- 5. Given the 100% objective primary endpoint we have decided not to use a doubleblind design. This will make the study logistics and therefore the inclusion of patients more straightforward. By offering state-of-the-art triazole resistance testing to all patients, the presence of triazole resistance is made very unlikely and therefore the treating physician can be reassured that the treatment given to patients in the control arm is a fully active treatment.

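### Endpoints 5 and 6 are fitted separately and never compared, so they cannot show whether the treatment effect differs between haematology and other patients

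*Protocol*

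**What the plan says.** Section 7.1.2 lists, as endpoint 5, six-week survival in non-ICU MITT patients with a haematological disease. Its complement is endpoint 6: "Overall survival 6 weeks after the start of therapy in the subgroup of non-ICU patients without an underlying haematological disease (MITT population"). Section 9.1 applies the primary analysis to endpoints 2 to 6, with a crude and an adjusted odds ratio for each: "The listed sub-populations will be analyzed using simple and multivariable logistic regression". The same section calls these analyses exploratory and makes no multiplicity adjustment. No section states a treatment-by-host interaction or any other comparison of endpoints 5 and 6.

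Three other places bear on how the pair will be read. Section 2 counts endpoints 1 to 6 among those that capture the primary objective. Section 7.1.3 explains why enrolment goes beyond the haematology-only population of the earlier randomised trial: "there is no reason to believe that the hypothesis of improved survival with combination therapy only applies to these patients". Section 7.2 stratifies randomisation by AML, GVHD and other, which is not the split used in endpoints 5 and 6.

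**The concern.** Extending the trial beyond haematology is a deliberate design choice that rests on the expectation in section 7.1.3. Endpoints 5 and 6 are the only prespecified endpoints that split patients by haematological status, so they are where a reader will look to see whether that expectation held. The natural question is whether the two effects differ. Separate fits answer another question: whether each group, at its own size, reaches significance.

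With unequal groups, one shared benefit can easily be significant in the larger group and not in the smaller. Without an estimate of the difference, that pattern invites the reading that the combination helps haematology patients only. At stake is the applicability of the result to the patients this trial adds to the earlier evidence.

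**Working it through.** **Inputs from the protocol.** Design effect (9.5): "We consider a 33% lower overall mortality with combination therapy (=from 35% to 23,33%) compared to monotherapy of clinical importance", a relative risk of 2/3. Size (9.5): "This leads to a sample size of 237 evaluable patients per group". Test level (9.3): "the primary endpoint will be tested at the α =0.05 level (two-sided test"). Allocation is 1:1 (7.2). For the earlier haematology-only trial (9.5): "the mortality in the voriconazole control group was 28% 6 weeks after the start of therapy".

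**Assumed inputs.** The protocol gives no haematology share. Section 10 says only that AML and allogeneic transplant patients will be the majority. Section 9.5 expects a small number of ICU patients, without a figure. I take haematology as 50-90% of non-ICU patients and ICU as 10% of the MITT, and vary both.

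**Formula.** For n per arm, power = Φ[(d − 1.96·SE0)/SE1], where d = p1 − p2, SE0 = √[2p̄(1−p̄)/n] and SE1 = √{[p1(1−p1) + p2(1−p2)]/n}.

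**The plan's own figure.** With n = 237 and 35% against 23.33%: d = 0.1167, SE0 = 0.0418, SE1 = 0.0414, and power = Φ(0.84) = 80.0%. The stated sample size reproduces.

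**Pattern probabilities.** The two groups share no patients, so with powers H (haematology) and N (the rest), P(haematology only) = H(1−N), P(neither) = (1−H)(1−N), P(both) = HN and P(rest only) = (1−H)N. With 10% ICU there are 237 × 0.9 = 213.3 non-ICU patients per arm. At an 80% share this gives 171 and 43 per arm, H = 66.1% and N = 21.7%, so P(haematology only) = 0.661 × 0.783 = 52%.

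Design rates in both groups, 10% ICU:

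| Haematology share of non-ICU | H | N | Haem. only | Neither | Both | Rest only |
|---|---|---|---|---|---|---|
| 50% | 47% | 47% | 25% | 29% | 22% | 25% |
| 60% | 54% | 39% | 33% | 28% | 21% | 18% |
| 70% | 60% | 30% | 42% | 28% | 18% | 12% |
| 80% | 66% | 22% | 52% | 27% | 14% | 7% |
| 90% | 71% | 13% | 62% | 25% | 9% | 4% |

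**When haematology only leads.** H(1−N) exceeds (1−H)(1−N) exactly when H is above 50%.
- At 35% control mortality this needs about 117 haematology patients per arm: 117/213.3 = 55% of non-ICU patients at 10% ICU. At 20% ICU and a 60% share, neither leads narrowly (33% against 32%).
- At 28% control mortality in both groups it needs about 158 per arm: 158/213.3 = 74% at 10% ICU, or 158/(237 × 0.95) = 70% at 5% ICU. At 10% ICU and shares of 60/70/80/90%, haematology only has probability 30/37/44/52% against 40/40/39/38% for neither.
- Suppose haematology is at 28% and the remaining patients, ICU included, have whatever rate makes the MITT average 35%. With h the haematology share of the whole MITT, that rate is (0.35 − 0.28h)/(1 − h), which is 45.5% at h = 60%. At 10% ICU and h = 60%, H = N = 46%: neither has probability 29%, haematology only 25% and rest only 25%. Haematology only leads from about h = 70% (32% against 29% for neither).

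**What an interaction term can deliver.** Take 360 haematology and 90 other patients (180 and 45 per arm), design rates in haematology and no benefit (35% in both arms) in the rest. The haematology log odds ratio is ln[(0.2333/0.7667)/(0.35/0.65)] = −0.571, and the other is 0. Variances are 1/(180×0.2275) + 1/(180×0.1789) = 0.0555 and 2/(45×0.2275) = 0.1954. The standard error of the difference is √0.2508 = 0.501, so z = 0.571/0.501 = 1.14 and power is about 21%. With the same benefit in both groups, the second variance is 1/(45×0.2275) + 1/(45×0.1789) = 0.222 and the standard error is √0.2774 = 0.527. The 95% interval for the ratio of odds ratios then runs from the estimate divided by 2.8 to the estimate times 2.8, since exp(1.96 × 0.527) = 2.8.

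All figures use unadjusted comparisons. Covariate adjustment would shift the powers slightly, not the pattern.

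**The case against.** The strongest reply is that nothing in section 9.1 is false. Fitting each subgroup is an ordinary way to obtain subgroup odds ratios, the analyses are labelled exploratory, and an interaction term often first appears in a statistical analysis plan, which may exist but is not shown. Much of this stands, and it limits the point to an improvement. It does not remove it. Section 9.1 already fixes the populations, the model and the covariates for these endpoints, and that method cannot address the question the split raises. The exploratory label warns against false positives, not against reading unequal power as a different effect.

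A second reply is that the interaction test would rarely reject. That is correct: about 21% power in the example even with no benefit in the smaller group. The gain lies in the ratio and its interval, which show how little the data can say about a difference.

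Three stronger readings are tempting and are not supported:
- A reader might infer that significance in haematology alone is the likeliest result whatever the case mix. The protocol gives no haematology share, and at lower shares or at 28% mortality another pattern leads.
- A reader might infer that the protocol intends to conclude benefit in haematology only. No section says so. Section 10 does attach a consequence to significance within one subgroup, but for AML, GVHD and other, and the consequence is only an exploratory cost-effectiveness analysis.
- A reader might infer that the non-haematology model is too small to estimate. The documents give no size for that group, section 9.1 limits the adjustment factors to those applicable, and a crude odds ratio is reported as well.

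**Conclusion.** The point holds in a limited form. Endpoints 5 and 6 are analysed apart, with no comparison, so they cannot show whether the effect differs by host; this is true at any split. How often the pair would mislead under a uniform one-third reduction depends on figures the protocol does not give. At the design rates, with 10% ICU and a 60-90% haematology share of non-ICU patients, significance in haematology alone occurs in about 33-62% of trials and is the most likely single pattern. At 28% control mortality it leads only from a share of about 70-74% (at 10% and 5% ICU, the higher threshold going with the larger ICU share). The primary analysis is unaffected.

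**What to change.** In section 9.1, analyse endpoints 5 and 6 in one logistic model on all non-ICU MITT patients, with treatment, haematology group, their interaction and the applicable covariates. Report from it the odds ratio in each group and the ratio of the two with its 95% confidence interval, and keep the crude counts per group. Add one sentence saying that a differing effect by host group will not be inferred from significance in one group and not in the other.

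The cost is a few lines of text, with no new data, patients or visits. There are two drawbacks. Covariate effects are assumed to be common to both groups. The interaction has low power, so it should be read as an estimate with its interval, and a non-significant interaction should not be taken as proof that the effects are equal.
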